## Study Visits:

[figure not shown]
Infants with early pulmonary hypertension will be randomized to the treatment group or the placebo group (see randomization plan). iNO or placebo treatment will start at 20 ppm. Treatment will continue for 2 weeks or until resolution of pulmonary hypertension, whichever comes first.

Current Version	9/10/2020	IRBNet #: 1170748
Date:		
Previous Version		Page 12 of 25
Date:		

To ensure the safety and evaluate the clinical response to iNO treatment, we will perform serial echocardiograms as shown in figure 2.

Figure 2

Time Line for Serial Echocardiography

\*PMA: Post Menstrual Age  
+ PH: Pulmonary Hypertension

Since the data of SpO2 & FiO2 are available in all infants, their ratios (SF ratio) will be calculated as markers of improved oxygenation. SF ratio has the advantage of avoiding invasive arterial blood sampling in situation when umbilical arterial line is unavailable. It is a reliable noninvasive surrogate for PaO2: FiO2 ratio to identify children with severe lung disease. Respiratory Severity Score (RSS= FiO2 X Mean airway pressure (MAP)) will be monitored for infants on mechanical ventilation since the data of mean airway pressure will be available. Significant response to iNO treatment will be defined as 20% improvement in SF ratio or resolution of pulmonary hypertension (assessed by echo) within 72 hours. Serial echocardiograms will be performed every 24-48 ± 12 hours until 14 days of life irrespective of the length of treatment.

Current Version 9/10/2020  
Date:

IRBNet #: 1170748

Previous Version  
Date:

Page 13 of 25

If PH is resolved during the 2-week treatment window or after the completion of the 2-week treatment protocol, we will start weaning the iNO dose by decreasing to 15 ppm. Weaning will continue to 10, 5, 4, 3, 2 and 1 ppm every 4 hours. During the weaning process if SF ratio decreased by 20%, iNO /Placebo dose will be increased to the minimum dose where  $\text{FiO}_2$  and  $\text{PaO}_2$  were stable. Weaning can be resumed after 12 hours following the above guidelines. The iNO weaning process described above is the current standard of care in our NICU for infants with PH. If pulmonary hypertension recurs in the first 2 weeks of life after stopping the treatment, iNO/Placebo treatment will be resumed based upon the randomization at the time of enrollment.

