About 1/3 of term and near-term infants with pulmonary hypertension may not respond to iNO. We will evaluate the effectiveness of iNO treatment by recording changes in serial echocardiogram and in mean airway pressure (MAP),  $\text{FiO}_2$ ,  $\text{SpO}_2/\text{FiO}_2$  ratio, and oxygenation index (OI) before and at  $24 \pm 6$ ,  $48 \pm 6$ , and  $72 \pm 12$  hours after beginning therapy. Non-responders will be defined as no improvement in pulmonary artery pressure or cardiac function on three serial echocardiograms and lack of 10% improvements from baseline for MAP,  $\text{FiO}_2$ ,  $\text{SpO}_2/\text{FiO}_2$  ratio and OI at  $72 \pm 12$  hours after starting treatment. Once an infant is identified as a non-responder, we will start weaning treatment (iNO or placebo) as described in our iNO weaning plan given below. It is important because even in "non-responders," one can still see significant rebound pulmonary hypertension with iNO discontinuation. If pulmonary hypertension is noted on subsequent echocardiograms, study intervention will not be resumed for non-responders. However, there is no restriction on clinical team to start iNO if needed based on clinical criteria.

During the course of hospitalization, all infants will receive standard of care and will be monitored as per NICU monitoring. Per AdventHealth NICU standardized guidelines, target oxygen saturations for  $\leq 32$  weeks PMA is 86-92%. We will follow these guidelines while the subject is receiving supplemental oxygen.

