## Study Outcome Measures (Endpoints)

- Maternal demographics (listed under the data collection section of the protocol)
- Infant measures (listed under the data collection section of the protocol)

Current Version Date:	9/10/2020	IRBNet #: 1170748
Previous Version Date:		Page 14 of 25

- Incidence of death or BPD measured at 36 weeks post menstrual age (yes or no)
  - BPD will be defined as need for supplemental oxygen for at least 28 days. Severity of BPD will be determined at 36 weeks postmenstrual age. Infants with no need for supplemental oxygen will be classified as mild BPD. Continued requirement for supplemental oxygen (<0.3 FiO2) will be considered moderate BPD. Infants requiring >0.3 FiO2 and or positive pressure respiratory support will be diagnosed with severe BPD. The need for continuing oxygen therapy will be determined by a room air challenge. We will prospectively collect data that will allow us to define BPD as recommended by the 2018 NICHD report
- Pulmonary arterial pressure based on serial echocardiograms)
- Oxygen saturation level (average for each 24-hour period after enrollment)
- Arterial pressure and oxygen saturation will be measured up to 2-weeks or until the treatment is discontinued, whichever is shorter.

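### The endpoints section ends arterial pressure and saturation measurement when treatment stops, against the Study Visits schedule; if applied, early resolvers have no 72-hour pulmonary artery pressure

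*Combined protocol and SAP*

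**What the plan says.** Four parts of the combined protocol and SAP bear on this.

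- **Study Outcome Measures (Endpoints)**, last bullet: "Arterial pressure and oxygen saturation will be measured up to 2-weeks or until the treatment is discontinued, whichever is shorter". It follows directly after the bullets on pulmonary arterial pressure and oxygen saturation.
- **Study Visits**, echo schedule: serial echocardiograms every 24-48 ± 12 hours, "until 14 days of life irrespective of the length of treatment". The section also plans for what happens "If pulmonary hypertension recurs in the first 2 weeks of life after stopping the treatment", which presupposes looking for it off treatment.
- **Study Visits**, effectiveness readings: echo, mean airway pressure, FiO2, SpO2/FiO2 and oxygenation index at 24 ± 6, 48 ± 6 and 72 ± 12 "hours after beginning therapy". No condition on still being treated is attached. SpO2 and FiO2 data, it says, "are available in all infants, their ratios (SF ratio) will be calculated as markers of improved oxygenation".
- **Secondary Objective** and **Secondary Objective Analysis**: the first compares arms on the change in pulmonary artery pressure and oxygenation from treatment start to about 72 hours. The second analyses PAP change at any time up to 72 hours. They do not name the same time point.

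Treatment length depends on response: "Treatment will continue for 2 weeks or until resolution of pulmonary hypertension, whichever comes first". On resolution the gas is first reduced to 15 ppm, and then: "Weaning will continue to 10, 5, 4, 3, 2 and 1 ppm every 4 hours".

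**The concern.** One section ties outcome measurement to treatment; another expressly does not. The cut-off stands in the endpoints section, where an analyst would look to see which data count.

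Treatment can end early because the infant has responded, so a cut-off at discontinuation would remove the 72-hour value from the quickest resolvers. Infants classed as non-responders keep theirs: that classification uses the 72 ± 12 hour readings, and their wean starts only afterwards. Whether a value is missing would then depend on response. If resolution is faster in one arm, which is what the trial hopes to show for iNO, it would also differ by arm.

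At stake is the only secondary objective. The analysis section does not say how a missing 72-hour value is handled. If its looser time frame were used to substitute earlier values, those would all predate gas off and could not show a recurrence after it.

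**Working it through.** There is no stated figure to reproduce; the check is a timeline. All inputs come from Study Visits.

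**1. Length of the wean.** Seven levels (15, 10, 5, 4, 3, 2, 1 ppm) at 4 hours each: 7 × 4 = 28 hours from the first reduction to gas off, if uninterrupted. The 1 ppm level is reached at 6 × 4 = 24 hours. A 20% fall in SF ratio interrupts the wean for at least 12 hours, giving at least 28 + 12 = 40 hours.

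**2. The 72-hour window.** 72 − 12 = 60 hours to 72 + 12 = 84 hours.

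**3. Latest resolution that leaves nothing in the window.** This is 60 minus the time from resolution to discontinuation. It assumes that the wean starts when resolution is seen and that treatment is not restarted.

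| Reading of discontinued | Hours after resolution | Latest resolution with no value in 60-84 h | Cut-off if resolved at the 24 ± 6 h echo (18-30 h) |
|---|---|---|---|
| Gas off, uninterrupted wean | 28 | 60 − 28 = 32 h | 46-58 h |
| Reaching 1 ppm | 24 | 60 − 24 = 36 h | 42-54 h |
| Gas off, one 12 h hold | 40 | 60 − 40 = 20 h | 58-70 h |
| Moment of resolution | 0 | 60 − 0 = 60 h | 18-30 h |

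**4. Who is affected with an uninterrupted wean.**

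- Resolved at the 24 ± 6 hour echo: gas off at 18 + 28 = 46 to 30 + 28 = 58 hours. That is 14 to 2 hours before the window opens, so the whole window is lost.
- Resolved at the 48 ± 6 hour echo: gas off at 42 + 28 = 70 to 54 + 28 = 82 hours. Between 70 − 60 = 10 and 82 − 60 = 22 of the window's 24 hours remain, so the reading can still be taken.

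**5. Echo timing.** The general interval of 24-48 ± 12 hours, counted from treatment start (an assumption), puts the first follow-up echo anywhere from 24 − 12 = 12 to 48 + 12 = 60 hours. An infant first scanned after 32 hours cannot be identified as resolved by then, so the number exposed also depends on which schedule is followed.

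**6. Size and direction of bias.** In one arm, let f be the fraction without a 72-hour value, L their mean change and M the mean change of the whole arm. The mean among infants with a value is (M − fL)/(1 − f) = M + [f/(1 − f)](M − L). The error in the comparison is the term [f/(1 − f)](M − L) for iNO minus the same term for placebo. The documents give no resolution rate, so f is unknown, and nothing on L, so its sign relative to M is unknown. If the early resolvers still do best at 72 hours and more of them are on iNO, the difference shrinks. If their later course is no better than average, there is no shift. If they rebound after gas off, it can move the other way.

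**7. With measurement independent of treatment status.** The 60-84 hour reading is scheduled for every randomised infant still alive and in the study, up to 34 + 34 = 68.

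**The case against.** The strongest reply is that Study Visits is the operational schedule and speaks directly to this case, while the conflicting rule is one loosely worded bullet. Staff who follow Study Visits lose nothing. Figure 2, the echo time line, is not shown in the text available and may make the schedule plain. This stands: a contradiction is established, an actual loss of data is not. But the figure would not remove the endpoints sentence, and the text does not say which section governs.

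Three narrower points also stand.

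- The rule that echoes continue regardless of treatment length covers echoes only. For saturation the conflict is by implication, with the 24, 48 and 72 hour readings. Saturation would in any case be available from routine NICU monitoring.
- The endpoints bullet does not contain the word pulmonary; that is an inference from its position.
- Rebound is collected as an adverse event, so it would not go wholly unseen.

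A reader might infer that the rule must bias the comparison towards no effect because it drops the best responders. The documents do not support that. It requires that the lost infants still do better than average at 72 hours, and the protocol itself foresees recurrence and rebound after gas off. A reader might also count safety stops as a loss working the other way. Under Data Collection and Follow-up for Withdrawn Subjects, withdrawn infants leave the final analysis whatever the endpoints bullet says, so that is a separate matter.

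**Conclusion.** The endpoints bullet is wrong as written. It contradicts Study Visits directly for echo-derived PAP and by implication for both measures at 72 ± 12 hours. If it were applied, infants resolved by about 32 hours would have no PAP in the 60-84 hour window that the secondary objective needs. The 32 hours rests on an uninterrupted 28-hour wean, no restart, and discontinuation meaning gas off; other readings give 20, 36 or 60 hours. Missing values would depend on response and might differ by arm. The number of infants and the size and direction of any bias cannot be obtained from the documents, and no loss arises from this rule if Study Visits is followed. The point concerns a secondary objective and mainly PAP. It should be corrected, and does not touch the primary outcome.

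**What to change.** In Study Outcome Measures (Endpoints), write pulmonary arterial pressure in the last bullet and delete the clause that ends measurement at treatment discontinuation. State instead that PAP and SpO2/FiO2 are recorded at the times scheduled under Study Visits whether or not the infant is on study gas, unless an echocardiogram is delayed or cancelled for instability (as Mitigation of Risks allows).

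In Secondary Objective and Secondary Objective Analysis, name one time point, 72 ± 12 hours after starting therapy. List the infants without that reading by arm and reason (off gas, safety stop, death, echo delayed or cancelled).

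Optionally, adjust the comparison for the baseline value and the randomisation strata. This is for precision only; an unadjusted comparison of change between randomised arms is also valid.

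The cost is wording. The readings and echoes are already scheduled under Study Visits, and no dose, weaning or stopping rule changes.

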## Data Management and Quality Plan

### Data de-identification

Each subject will be assigned a unique study identification number (001, 002, 003, etc.) for data collection. A master list will be created to link the subject's MRN with the study number. The master list will be saved electronically in a password protected file on an AdventHealth server accessible only to study team members.

### Data Confidentiality, Storage, and Retention

Study documentation and paperwork will be stored in the locked Pediatric Research office and access will be restricted to the research team. The data file will be stored electronically on a password protected secure server at AdventHealth accessible only to the study team. Study documentation will be retained for 7 years after completion of the study. After that period, paper records will be placed in hospital approved shred bins. Electronic records will be placed in a computer electronic trash bin followed by immediate emptying of the electronic trash bin.

### Data Quality

Quality control procedures for this research study include source data verification by randomly selecting 10% of subject records with comparison between the paper case report form (CRF) and the electronic database record of those same data. If errors are common, data will be completely checked prior to data analysis.

Current Version Date:	9/10/2020	IRBNet #: 1170748
Previous Version Date:		Page 15 of 25

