### Study Site(s)/Location(s) and Number of Subjects

This is a single site clinical study to be conducted at the Neonatal Intensive Care Unit of AdventHealth for Children. A total of 136 infants will be enrolled in the trial, and 68 of those infants will be randomized (34 in each arm). Screen failures, which are defined as infants who were consented but the echocardiogram showed no PH, will be enrolled into the comparison group and no further intervention will occur for them. To compare the incidence of death or BPD, outcome data will continue to be collected on the comparison group for the duration of their hospital stay.

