### **Data Collection:**

Demographic and clinical data will be prospectively collected from maternal and neonatal charts along with data from serial echocardiograms. Following variables will be included in the database

- **Maternal Data:** Age, ethnicity, educational level, smoking, alcohol or illicit use of drugs, medication history, any medical or surgical problem, antenatal screening lab results (GBS, HIV, HBs Ag, RPR) maternal UTI, chorioamnionitis, rupture of membrane, vaginal bleeding or discharge, antenatal antibiotics, steroids, indomethacin or magnesium.
- **Neonatal Data: BPD our primary outcome is determined based on the need for positive pressure ventilation or supplemental oxygen after room air challenge test**  
Gestation, Gender, mode of delivery, Apgar scores, IUGR, Birth Weight, Surfactant, Ventilation, pulmonary hypertension (early, intermittent or late), use of supplemental oxygen, culture proven infections, blood transfusions, Cardiotropic medication, bicarb infusion, saline boluses, use of indomethacin, PDA treatment/ ligation, use of diuretics, use of postnatal steroids, IVH, PVL, Post IVH hydrocephalus, NEC, ROP, ROP requiring treatment, VP shunt, Tracheostomy, Gastrostomy tube, home oxygen, home ventilation, length of hospital stay and death.

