## Sample Size Determination

Sample size was calculated based on our pilot study showing that the incidence of death or BPD among extremely preterm infants with early pulmonary hypertension was 80%. Assuming a 30% relative decrease of the incidence we came up with a sample size of 34 infants in each arm with 80% power and alpha of 0.05.

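### The check labelled source data verification compares the CRF with the database in 10% of records; no check of the BPD fields against the chart is described

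*Combined protocol and SAP*

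**What the plan says.** The Data Quality section describes one verification procedure: "source data verification by randomly selecting 10% of subject records with comparison between the paper case report form (CRF) and the electronic database record". Its escalation rule reads: "If errors are common, data will be completely checked prior to data analysis". It gives no threshold for what counts as common, and it does not say what a complete check would compare.

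The Data Collection section states where the data come from: "Demographic and clinical data will be prospectively collected from maternal and neonatal charts along with data from serial echocardiograms". The chart and the echocardiogram are therefore the source, and the CRF is a transcription of them.

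The Study Outcome Measures section makes the primary outcome a yes/no record of death or BPD at 36 weeks postmenstrual age. BPD status has to be assembled from several chart items: days on supplemental oxygen, inspired oxygen and respiratory support at 36 weeks, and a bedside test ("The need for continuing oxygen therapy will be determined by a room air challenge"). No section describes comparing these CRF entries with the chart, or adjudicating the outcome.

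**The concern.** Source data verification ordinarily means comparing recorded study data with the source. Here the two items compared are the CRF and an electronic copy of the CRF. The comparison finds typing errors made between those two. It cannot find a miscounted number of oxygen days or a room air challenge result misread when the CRF was filled in, because both copies then carry the same wrong value.

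The escalation rule does not close the gap. It is triggered by mismatches between CRF and database, so it can stay silent however many abstraction errors there are.

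At stake is the primary comparison: a count of yes/no outcomes in 34 v 34 infants, where a change of one can move the result across the significance boundary.

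**Working it through.** **1. Which transfer steps are checked**

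| Step | Check described |
|---|---|
| Chart to CRF, BPD fields | None |
| Chart to CRF, death | No CRF check, but a separate route: death is a listed adverse event collected to 36 weeks and documented in the chart, reported to the PI and coordinator within 24 hours and reviewed by the medical monitor (Adverse Event Reporting) |
| CRF to database | 10% of subject records (Data Quality) |

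**2. How many randomised infants the sample reaches**

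The Study Sites and Number of Subjects section gives 136 enrolled and 68 randomised, 34 per arm. The sampling frame is not stated, so both readings are shown.
- Frame of 68: 0.10 × 68 = 6.8, about 7.
- Frame of 136: 0.10 × 136 = 13.6, about 14. The expected number randomised is 14 × 68/136 = 7.

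Either way about 68 − 7 = 61 randomised infants are outside the sample.

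A chart-based check at the same 10% would still be thin. It would include one given misclassified infant with probability 7/68 = 10.3%. For at least one of two the probability is 1 − (61 × 60)/(68 × 67) = 19.7%.

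**3. What one infant can do to the primary result**

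Inputs from Sample Size Determination: 80% on placebo and a 30% relative decrease, so 0.80 × 0.70 = 56% on iNO. Expected events are 0.80 × 34 = 27.2 and 0.56 × 34 = 19.0, rounded to 27 v 19. The planned 34 per arm is taken as given. It does not reproduce from the stated inputs (80% v 56% at 80% power needs 59 per arm two-sided or 46 one-sided), but that is a separate matter and nothing here depends on it.

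Uncorrected Pearson chi-square, with a and c events on placebo and iNO and b and d non-events:

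χ² = 68(ad − bc)² / [34 × 34 × (a + c) × (b + d)]

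- 27 v 19: 68 × (27×15 − 7×19)² / (1156 × 46 × 22) = 68 × 272² / 1,169,872 = 4.30, p = 0.038
- 27 v 20: 68 × (27×14 − 7×20)² / (1156 × 47 × 21) = 68 × 238² / 1,140,972 = 3.38, p = 0.066
- 26 v 19: 68 × (26×15 − 8×19)² / (1156 × 45 × 23) = 68 × 238² / 1,196,460 = 3.22, p = 0.073

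The planned relative risk behaves the same way. For 27 v 19, RR = 19/27 = 0.70 and SE(ln RR) = √(1/19 − 1/34 + 1/27 − 1/34) = 0.176, so the upper 95% limit is exp(−0.351 + 1.96 × 0.176) = 0.99. For 27 v 20, RR = 0.74 and the upper limit is 1.03.

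The boundary depends on the test. With Fisher it lies between 27 v 18 (p = 0.039) and 27 v 19 (p = 0.068). With Yates the same two tables give 0.040 and 0.070.

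**4. How often a result lies that close**

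Summing Bin(a; 34, 0.80) × Bin(c; 34, 0.56) over every table whose significance at 0.05 changes when one infant in either arm is reclassified gives about 23%, by uncorrected chi-square or by Fisher.

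**The case against.** **Other checks are not excluded.** The Data Quality section says its procedures include this check, and the Study Agent section commits the trial to FDA requirements and ICH-GCP. A reader might infer that abstraction errors can never be found. The documents do not support that: they show that no chart check is described, not that none will take place. The objection stands to that extent, but a general commitment does not say which fields are checked, in whom, or when.

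**Death has another route.** A reader might infer that both components of the outcome are equally exposed. They are not. Prompt reporting and medical monitor review give a missed death a separate way to surface, so the gap concerns mainly BPD.

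**The sampling frame is open.** A reader might take it that half of the sample is spent on the comparison group without early PH. The protocol refers only to subject records, so this is not established. The figure of about 7 randomised infants does not depend on it.

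**The fragility example is one table.** The expected counts lie next to the boundary for uncorrected chi-square, and the plan does not say whether a correction applies. With Fisher or Yates, 27 v 19 is already non-significant. The opposite one-infant moves strengthen the result: 28 v 19 gives p = 0.018 and 27 v 18 gives p = 0.021. Any small binary trial has tables near the boundary. All of this is correct and limits the claim to what an error could do.

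**Masked errors should not favour an arm.** Probably so, but non-differential misclassification of a binary outcome generally dilutes a real effect, and a trial of this size has little room for dilution.

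**Conclusion.** The concern holds in a limited form. The label does not match the procedure: the described check tests data entry in about 7 of 68 randomised infants, and it cannot detect abstraction errors in the fields that determine BPD. The escalation rule does not repair this, because it responds only to data-entry mismatches.

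A reader might go further and conclude that the primary result will be wrong or will turn on one infant. The documents give no error rate, so that does not follow. The 23% in the working is the chance, at true rates of 80% v 56% with 34 per arm, that a result lies within one infant of the boundary. It is not the chance that a misclassification occurs.

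The change is worth making because the remedy is small and the outcome is assembled from several chart items. It is an improvement to the data quality plan and does not by itself invalidate the trial.

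**What to change.** Amend the Data Quality section as follows.

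- Before unmasking, the existing research team verifies the primary-outcome fields against the medical record for all 68 randomised infants: death, days on supplemental oxygen, respiratory support at 36 weeks and room air challenge result at 36 weeks.
- Keep the 10% CRF-to-database comparison for the remaining fields, and call it a data-entry check.
- In the same edit, state what error frequency counts as common and what the complete check then compares.

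The cost is some coordinator hours for a few fields in 68 charts at a single site. Treatment, endpoint and sample size are unchanged.

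One related matter has to be settled separately. The Data Collection section bases BPD on the need for positive pressure or oxygen after a room air challenge. The Study Outcome Measures section bases it on at least 28 days of oxygen, with a mild grade for infants off oxygen at 36 weeks. These must be reconciled so that the verified fields map to one yes/no outcome; chart verification alone does not settle which infants count as events.
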